ECT is used in approximately 5% of all psychiatric patients in Denmark with slightly increasing frequency of 11% since 1999. ECT acts through epileptic seizures and have a documented anti-kindling effect involving limbic and paralimbic structures. This kindling repressing effect is probably of significance for the mechanism of ECT. rTMS does not work by inducing seizures, but like ECT low frequency rTMS has been shown to inhibit amygdala-kindled seizures in animal studies. Therefore, theoretically it is possible that low frequency rTMS can amplify the antidepressant effect of ECT.

The present study will be carried out to investigate in which degree right prefrontal low frequency rTMS administered as add-on may accelerate the

antidepressant effect of ECT and thus minimize the side-effects of this treatment.

Material and methods

Design

The present study will be carried out as a randomized, clinically controlled, double blind investigation comparing conventional ECT + sham-stimulation with ECT + right prefrontal low frequency rTMS. Previous research concerning the antidepressant effect of ECT versus rTMS has found remission rates on ECT between 50 and 60%. On the basis of these figures and the outcome of previous RCT studies on the antidepressant effect of low frequency rTMS compared to placebo the difference in the incidence of remission was expected to be 20-30%. A rate difference of 20% would require 81 patients, while a rate difference of 30% would require 31 patients in each group to have 80% power in a 2-sided test at a 5% significance level.

Randomization

The patients are randomly allocated to ECT + rTMS or ECT + sham According to the principle of block randomization. Six blocks are created with 10 sealed opaque envelopes in each, half of them containing a treatment code for rTMS and the other half for ECT. The envelopes in each block are shuffled thoroughly and numbered from one to 10. To ensure allocation concealment, the patients were randomly allocated to treatment by an independent third part.

Ethics

The study meet the criteria of the Helsinki Declaration II. The patients' consent is based on written and oral information, and the regional ethics committee approved the project protocol.

Study Population

The study population covers inpatients with depression from the County of

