Aarhus. The patients are admitted to the department for Depression and Anxiety, Aarhus University Hospital, Risskov, Denmark, and recruited primarily from the city of Aarhus with associated rural districts, a catchment area of approximately 300,000 inhabitants.

Inclusion criteria:

Age between 18 and 80 years and a total score on 17-item HAM-D (24) of 20 or higher and/or 9 or higher on the subscale.

All patients fulfill the ICD-10 criteria for moderate to severe depression and the Diagnostic and Statistical Manual of Mental Disorders-IV criteria for major depressive disorder. Unipolar as well as bipolar patients are included.

Exclusion criteria:

Patients with organic brain damage, personal or family history of epileptic seizures, metallic objects in the chest or brain, cardiac pacemakers, and somatic diseases associated with brain dysfunction were excluded from the study. Pregnancy, use of coercive measures, severe suicidal risk, severe agitation or delirium, and alcohol or drug dependence (ICD-10) constituted additional exclusion criteria.

General physical and neurological examination will be supplied by routine blood tests and an electrocardiogram.

Outcome measures

Primary effect measures: percentage of response and remission.

Secondary outcome measures: change in cognitive function.

Depression severity is evaluated using the Hamilton 17-item, the 6-item scale for depression (HAM-D6) and the Major Depression Inventory scale (MDI)

Response defined as a 50 % reduction in total HAM-D score and remission as a total HAM-D (17-item) score of 8 or lower.

Adverse effect is further assessed by a scale based on the Udvalg for Kliniske Undersøgelser (UKU: Committee for Clinical Investigations) side effect rating scale

Changes in the degree of depression and adverse effects will be assessed at baseline (before treatment) at weekly intervals within 24 hours after 3. 6. and 9. ECT. Additional HAM-D, MDI's and UKU ratings are carried out 4 weeks after termination of the treatment period. Trained clinicians carry out quantitative and diagnostic ratings.

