The coil, which is identical on both sides, had a built-in position sensor used to ensure that the correct (active or sham) side of the coil faced towards the patient's head. If the coil position is wrong, the operator receive the display message a "Flip Coil" prompt on the MagPro screen. To ensure blinding of patients, electrodes from the MagPro will be used to stimulate the patient's skin in the coil area to mimic real rTMS.

Electroconvulsive Therapy

Thymatron (Fred Berninger Import OHG, Taufkirchen, Germany) (maximum dose of stimulation, 1008 milli coulombs) is used for ECT. Patients elected for this type of treatment received 9 ECTs on the average during the project period. The treatment is administered 3 times weekly with handheld electrodes according to the guidelines of the Danish Psychiatric Society .

Statistics

Treatment and placebo groups will be compared based on a t-test or chi-square test dependent on which was most suitable. The effect of treatment on HAMD₆, HAM-D₁₇ and MDI over time will be evaluated based on a last observation carried forward as well as quadratic linear mixed model. The effect of treatment on cognitive function over time will be evaluated based on a linear mixed model.

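### Optional, low-cost gain for remission only: the one planned test that fits it is an unadjusted chi-square, although baseline HAM-D17 is already collected and could be a prespecified covariate

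*Combined protocol and SAP*

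**What the plan says.** Under Outcome measures the plan states: "Primary effect measures: percentage of response and remission". It defines "remission as a total HAM-D (17-item) score of 8 or lower", an absolute cut-off; response is a halving of the HAM-D score. Depression severity, with HAM-D17 among the scales, is "assessed at baseline (before treatment) at weekly intervals within 24 hours after 3. 6. and 9. ECT".

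The Statistics section gives one sentence on the comparison of groups: "Treatment and placebo groups will be compared based on a t-test or chi-square test dependent on which was most suitable". It names no outcome and no covariate. The carried-forward and mixed-model analyses that follow are for the three depression scales over time, with a further mixed model for cognition. None is assigned to remission. That the chi-square is the remission test is therefore an inference, but no other listed method suits a yes/no outcome.

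Under Design, earlier work "has found remission rates on ECT between 50 and 60" percent, and a gain of 20 to 30 points is expected. "A rate difference of 20% would require 81 patients" per group, and 30 points would require 31, at 80% power and two-sided 5%. Under Randomization, "Six blocks are created with 10 sealed opaque envelopes in each", split equally between the arms; stratification by severity is not described.

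**The concern.** Remission requires every patient to reach the same final score, so a patient who starts higher has further to fall. If baseline HAM-D17 predicts remission, an unadjusted comparison leaves that part of the variation in the error term, and simple blocks do not balance it by design. Response is already scaled to each patient's baseline, so no gain is claimed there.

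At stake is efficiency only. With about 30 per arm, a modest gain that needs no extra patient, visit or rating deserves consideration, and a covariate is credible only if it is named before the data are seen.

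**Working it through.** **1. The plan's own figures.** Inputs from Design: 60% control remission (upper end of the quoted range), 80% or 90% with rTMS, two-sided 5%, 80% power. Per group, n = [1.96·√(2p̄(1−p̄)) + 0.8416·√(p₁(1−p₁) + p₂(1−p₂))]² / d².

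- 60 vs 80%: p̄ = 0.70; (1.96 × 0.648 + 0.8416 × 0.632)² / 0.04 = 81.2 (stated: 81).
- 60 vs 90%: p̄ = 0.75; (1.96 × 0.612 + 0.8416 × 0.574)² / 0.09 = 31.5 (stated: 31).

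Both reproduce to within rounding, so the sizing agrees with an unadjusted two-proportion test.

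**2. Power with the envelopes available.** 6 × 10 = 60 envelopes, or 30 per arm. Power = Φ{[d√n − 1.96·√(2p̄(1−p̄))] / √(p₁(1−p₁) + p₂(1−p₂))}.

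- 60 vs 80%: Φ[(1.095 − 1.270) / 0.632] = Φ(−0.28), about 39%.
- 60 vs 90%: Φ[(1.643 − 1.200) / 0.574] = Φ(0.77), about 78%.

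**3. Gain from adjustment (simulation).** Assumption: remission arises from a latent normal outcome with correlation r to baseline. The documents give no r, so a range is shown. Set-up: 60% control remission, six blocks of 10, 30 per arm, 2,000 within-block permutations of treatment; 40,000 trials per row (20,000 for 60 vs 90%). The adjusted test statistic is the difference between arms in mean residual from a logistic model of remission on baseline alone.

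The observed correlation between baseline and the yes/no outcome is smaller than r, by the factor φ(z)/√(p(1−p)): 0.386/0.490 = 0.79 at 60% remission and 0.280/0.400 = 0.70 at 80%.

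| Latent r | Observed r at 60% / 80% | Chi-square power, 60 vs 80 | Adjusted power, 60 vs 80 | Change, 60 vs 80 (points) | Variance ratio, 60 vs 80 | Change, 60 vs 90 (points) |
|---|---|---|---|---|---|---|
| 0 | 0 / 0 | 39.1% | 38.5% | −0.6 | 1.020 | −1.5 |
| 0.2 | 0.16 / 0.14 | 39.1% | 39.5% | +0.3 | 0.994 | −0.5 |
| 0.3 | 0.24 / 0.21 | 39.1% | 40.5% | +1.4 | 0.973 | +1.3 |
| 0.4 | 0.32 / 0.28 | 39.1% | 42.1% | +3.0 | 0.926 | +2.6 |
| 0.5 | 0.39 / 0.35 | 39.2% | 44.1% | +4.9 | 0.870 | +4.9 |
| 0.6 | 0.47 / 0.42 | 39.3% | 47.2% | +8.0 | 0.807 | +7.6 |

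Changes are paired differences (standard error 0.1 to 0.2 points), so they can differ by 0.1 from the rounded columns. The variance ratio is adjusted over unadjusted risk difference. At r = 0.5 it is worth 30/0.870 = 34 patients per arm, and at 0.6 it is worth 30/0.807 = 37.

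Two smaller repeat simulations (8,000 and 4,000 trials per row) gave, at r = 0, 0.3, 0.5 and 0.6:

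- 60 vs 80%: −0.7 to −0.8, +1.0 to +1.6, +4.8 to +5.1, and +8.9 to +9.0 points.
- 60 vs 90%: −1.4 to −1.7, +0.4 to +0.5, +4.3 to +4.6, and +6.9 to +7.5 points.

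**4. Validity.** With 60% remission in both arms, the chi-square rejects in 4.7 to 5.0% of trials and the permutation test in 4.8 to 5.1%. An ordinary likelihood-ratio p-value from the adjusted model rejects in 5.3 to 5.9%, hence the permutation. The 95% interval for the standardised risk difference covers 94.0 to 94.6%. All 30 patients in an arm remit with probability 0.9³⁰ = 4.2% at a 90% rate and 0.8³⁰ = 0.1% at 80%.

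**The case against.** The strongest reply is that nothing here is broken. The chi-square is valid under randomisation and matches the sizing, the title calls the study a pilot, and HAM-D17 already receives a longitudinal model. The benefit rests on a correlation that the documents do not give, and it turns into a small loss if baseline is unrelated to remission. All of that stands, which is why the point is optional; the longitudinal model, however, does not analyse remission.

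A reader might infer more, in four ways that the documents do not support.

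- *That the trial is badly underpowered and adjustment rescues it.* The 39% applies to a 20-point difference. The plan expects 20 to 30 points, and at 30 points power is about 78%. The documents do not state 60 as the sample size; it is inferred from the envelopes.
- *That the table can be entered with an observed baseline-remission correlation.* Its r is latent. An observed 0.3 is a latent 0.3/0.79 = 0.38 to 0.3/0.70 = 0.43, so it belongs near the row with about +3 points.
- *That the severity threshold truncates baseline by a known amount, so that the gain can be scaled down.* Entry requires at least 20 on HAM-D17 and/or at least 9 on the subscale. Read as written, a patient below 20 can enter, so there is no clean cut. The rule may narrow the range and lower r, but by how much cannot be worked out.
- *That the change costs nothing but wording.* It needs some programming, and it brings the drawbacks listed with the fix.

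**Conclusion.** The point holds as an optional improvement for remission alone. The plan makes no use of baseline HAM-D17 in the only test that fits this primary measure. With 30 per arm, using it would change power by about −0.6 to −1.5 points at latent r = 0, about +1 at 0.3 (observed about 0.21 to 0.24), about +5 at 0.5 (observed about 0.35 to 0.39) and about +8 at 0.6 (observed about 0.42 to 0.47). Observed values are for 60% and 80% remission.

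This rests on an assumed r, a latent normal outcome, 60% control remission and the inferred 30 per arm. Even at r = 0.6, power for a 20-point difference is about 47%, and the precision is that of 37 per arm against the 81 stated. It would be wrong to call the chi-square an error.

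**What to change.** Prespecify for remission a logistic regression on treatment and continuous baseline HAM-D17, reported as a standardised risk difference with 95% confidence interval; this keeps the scale used for sizing. Take the two-sided 5% p-value by permuting treatment within the randomisation blocks, using residuals from the baseline-only logistic model. That model does not contain treatment, so the p-value can still be computed when every patient in an arm remits. Name one fallback for the estimate in advance: if an arm has all or no remitters, report the unadjusted risk difference with a score-based interval. Keep the chi-square as supporting and leave the remission definition unchanged.

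Cost: SAP wording and modest extra programming; the data are already collected. Drawbacks: a small power loss if baseline is unrelated to remission; interval coverage of about 94%; a p-value and interval from different procedures, which may occasionally disagree; and a different test from the one used for response.

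Which rating time defines remission and how missing ratings are handled are separate points, and this change does not settle them.
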